6 ANALYSIS POPULATIONS

6.1 Intention-to-Treat (ITT) Population:

For Secondary Objective 3 and Exploratory Objectives 4 and 8, the primary analysis population will be the ITT Population; defined as all subjects who are randomized and vaccinated (received at least one study vaccine).

6.2 Modified Intention-to-Treat (mITT) Population:

For Primary Objective 1, Secondary Objectives 1 and 2, and Exploratory Objectives 1, 2, 3, 5 and 6 the primary analysis population will be the mITT Population; defined as all subjects who are randomized, vaccinated (received at least one study vaccine), and provide at least one day of complete data on the symptom diary.

6.3 Immunogenicity Population

For Exploratory Objective 7 (immunogenicity analyses) the primary analysis population will be the Immunogenicity Population defined as subjects who received study vaccines, provide baseline and Visit 4 blood draws of acceptable volume and quality within the protocol-defined time frame with no protocol violations affecting immunogenicity.

Protocol Violations for Exclusion from Immunogenicity Populations:

1. Did not receive both RZV Dose 1 and influenza vaccine.
2. No pre- and/or post-vaccination blood draw.
3. Vaccine administered outside of the vaccination window ($\pm 1-2$ weeks).
4. Receipt of any other vaccine between the pre- and post-vaccination blood draws.
5. New immunosuppression disorders between the pre- and post-vaccination blood draws or receipt of immunosuppressive medication between the pre- and post-vaccination blood draws.
6. Subject who was inadvertently enrolled and randomized to the study, though they were later learned to have had met criteria for study exclusion that would have affected immunogenicity.

7 BASELINE DATA AND FLOW CHART

7.1 Presentation of Baseline Data

The following baseline information will be presented by treatment group: age, sex at birth, ethnicity, race, employment status, highest education level, and if the participant lives alone. Summary statistics (e.g., mean, standard deviation, interquartile range) will be presented for continuous variables. Categorical variables will be described with frequencies and percentages. Other common conditions will be presented as a part of the manuscript's Table 1 and will be further broken down by site.

Common Conditions for Table 1.

- A. Cardiac and Pulmonary Conditions Affected by Influenza in Older Adults
 - a. Hypertension
 - b. Coronary Artery Disease
 - c. Congestive Heart Failure
 - d. Atrial Fibrillation
 - e. Valvular Heart Disease
 - f. COPD
 - g. Asthma
- B. Common Conditions in Older Adults Reported in Clinical Trials
 - a. Hyperlipidemia
 - b. Diabetes mellitus
 - c. Hypothyroidism
 - d. Osteoarthritis
 - e. Hearing Loss
 - f. Depression
 - g. Gastroesophageal Reflux Disease
 - h. End Stage Renal Disease
- C. Statin Use

7.2 Flow Chart

The number of enrolled participants will be presented in a flow chart by treatment group along with a breakdown of the two analysis populations.

8 ANALYSIS OF STUDY OBJECTIVES

8.1 Primary Objective

1. To compare the proportion of older adults with at least one severe (Grade 3) solicited local or systemic reactogenicity event after RZV dose 1 in the RZV and allV4 group vs. RZV and HD-IIV4 group

- Hypothesis: The proportion of participants with at least one severe (Grade 3) solicited reactogenicity event after RZV dose 1 will be noninferior (not higher) in the RZV and allV4 group compared with the RZV and HD-IIV4 group

This objective will be assessed in the mITT Population using a one-sided site-stratified noninferiority test with the alpha level set at 0.025 and noninferiority margin of 10%. The null hypothesis is simultaneous vaccination with RZV and allV4 is inferior (i.e., RZV and allV4 will have a higher proportion) to RZV and HD-IIV4 with regard to the proportion of adults with at least one severe (Grade 3) solicited local or systemic reactogenicity event on days 1-8 after RZV dose 1.

$$H_0: RZV \text{ and allV4} - RZV \text{ and HD-IIV4} \geq 0.10 \text{ (10\%)}$$

The alternative hypothesis is RZV and allV4 is noninferior to RZV and HD-IIV4 with regard to the proportion of adults with at least one severe (Grade 3) solicited local or systemic reactogenicity event after RZV dose 1.

$$H_a: RZV \text{ and allV4} - RZV \text{ and HD-IIV4} < 0.10 \text{ (10\%)}$$

The upper bound of a site-stratified Newcombe binomial confidence interval with Cochran-Mantel-Haenszel (CMH) weighting of the difference will be used to make this assessment.

This information is captured on the symptom diary CRF in the REDCap database. The grading criteria for injection site pain is provided in Tables 1 and 2.

Table 1. Injection-site Reactogenicity

Symptom	Mild (Grade 1)	Moderate (Grade 2)	Severe (Grade 3)
Pain	Any pain neither interfering with nor preventing normal every day activities.	Painful when limb is moved and interferes with every day activities.	Significant pain at rest. Prevents normal every day activities.
Induration/ Swelling	$\geq 20 \text{ mm to } \leq 50 \text{ mm diameter}$	$> 50 \text{ mm to } \leq 100 \text{ mm diameter}$	$> 100 \text{ mm diameter}$
Erythema (Redness)	$\geq 20 \text{ mm to } \leq 50 \text{ mm diameter}$	$> 50 \text{ mm to } \leq 100 \text{ mm diameter}$	$> 100 \text{ mm diameter}$

Table 2. Systemic Reactogenicity

Systemic	Mild (Grade 1)	Moderate (Grade 2)	Severe (Grade 3)
Fever (°C)	$\geq 37.5 - < 38.4^\circ \text{C}$ $\geq 100.0 - < 101.1^\circ \text{F}$	$\geq 38.4 - < 39^\circ \text{C}$ $\geq 101.1 - < 102.2^\circ \text{F}$	$\geq 39^\circ \text{C}$ $\geq 102.2^\circ \text{F}$

Table 1. Injection-site Reactogenicity

Fatigue/ Malaise	Fatigue that is easily tolerated	Fatigue that interferes with normal activity	Fatigue that prevents normal activity
Myalgia	Myalgia that is easily tolerated	Myalgia that interferes with normal activity	Myalgia that prevents normal activity
Arthralgia	Arthralgia that is easily tolerated	Arthralgia that interferes with normal activity	Arthralgia that prevents normal activity
Headache	Headache that is easily tolerated	Headache that interferes with normal activity	Headache that prevents normal activity
Gastrointestinal symptoms (nausea, vomiting, diarrhea, and/or abdominal pain)	Gastrointestinal symptoms that are easily tolerated	Gastrointestinal symptoms that interfere with normal activity	Gastrointestinal symptoms that prevent normal activity
Chills/Shivering	Shivering that is easily tolerated	Shivering that interferes with normal activity	Shivering that prevents normal activity

This information will also be presented by age-group for the subset of subjects aged 65-69 versus those subjects aged 70 years or older. No formal statistical hypothesis testing (i.e., no p-values) will be performed, only the confidence boundary of the difference will be presented.

8.2 Secondary Objectives

1. To compare the proportion of participants with at least one severe (Grade 3) solicited local reactogenicity event on days 1-8 after RZV dose 1 in the RZV and allIV4 group vs. RZV dose 1 and HD-IIV4 group.

The proportions of participants with at least one severe (Grade 3) solicited local reactogenicity event on days 1-8 after RZV dose 1 in the mITT Population will be compared between vaccine groups using the same statistical methodology as for Primary Objective 1. A one-sided site-stratified noninferiority test to determine if RZV dose 1 and allIV4 is noninferior to RZV dose 1 and HD-IIV4 with the alpha level set at 0.025 and a 10% noninferiority margin.

This information will also be presented by age-group for the subset of subjects aged 65-69 versus those subjects aged 70 years or older. No formal statistical hypothesis testing (i.e., no p-values) will be performed, only the confidence boundary of the difference will be presented.

2. To compare the proportion of participants with at least one severe (Grade 3) solicited systemic reactogenicity event on days 1-8 after RZV dose 1 in the RZV and allIV4 group vs. RZV dose 1 and HD-IIV4 group.

The proportions of participants with at least one severe (Grade 3) solicited systemic reactogenicity event on days 1-8 after RZV dose 1 in the mITT Population will be compared between vaccine groups using the same statistical methodology as for Primary Objective 1. A one-sided site-stratified noninferiority test to determine if RZV dose 1 and

allV4 is noninferior to RZV dose 1 and HD-IIV4 with the alpha level set at 0.025 and a 10% noninferiority margin.

This information will also be presented by age-group for the subset of subjects aged 65-69 versus those subjects aged 70 years or older. No formal statistical hypothesis testing (i.e., no p-values) will be performed, only the confidence boundary of the difference will be presented.

3. To compare the proportion of participants with at least one serious adverse event or adverse event of clinical interest after RZV dose 1 in the RZV and allV4 group vs. RZV dose 1 and HD-IIV4 group through Day 43 and describe these events.

The proportion and 95% exact binomial confidence interval, as well as the difference between vaccine groups and a 95% confidence interval of the difference in proportions, in the ITT Population of serious adverse events and events of clinical interest through Day 43 will be presented by site, vaccine group, and relatedness. Listings of the serious adverse events will also be presented. Adverse events of clinical interest include syncope during post-vaccination monitoring in clinic, anaphylaxis in the first 24 hours after immunization, and new onset immune-mediated disease as defined in Appendix A.

8.3 Exploratory Objectives

1. To compare the proportion of participants with at least one severe (Grade 3) solicited local or systemic reactogenicity event on days 1-8 after RZV dose 2 in the RZV and allV4 group vs. RZV and HD-IIV4 group.

The proportions of participants with at least one severe (Grade 3) solicited local or systemic reactogenicity event on days 1-8 after RZV dose 2 in the mITT Population will be compared between vaccine groups using the same statistical methodology as for Primary Objective 1. A one-sided site-stratified noninferiority test to determine if RZV dose 2 and allV4 is noninferior to RZV dose 2 and HD-IIV4 with the alpha level set at 0.025 and a 10% noninferiority margin.

This information will also be presented by age-group for the subset of subjects aged 65-69 versus those subjects aged 70 years or older. No formal statistical hypothesis testing (i.e., no p-values) will be performed, only the confidence boundary of the difference will be presented.

2. To compare the proportion of participants with at least one severe (Grade 3) solicited local reactogenicity event on days 1-8 after RZV dose 2 in the RZV and allV4 group vs. RZV and HD-IIV4 group.

The proportions of participants with at least one severe (Grade 3) solicited local reactogenicity event on days 1-8 after RZV dose 2 in the mITT Population will be compared between vaccine groups using the same statistical methodology as for Primary Objective 1. A one-sided site-stratified noninferiority test to determine if RZV dose 2 and allV4 is noninferior to RZV dose 2 and HD-IIV4 with the alpha level set at 0.025 and a 10% noninferiority margin.

This information will also be presented by age-group for the subset of subjects aged 65-69 versus those subjects aged 70 years or older. No formal statistical hypothesis testing (i.e., no p-values) will be performed, only the confidence boundary of the difference will be presented.

3. To compare the proportion of participants with at least one severe (Grade 3) solicited systemic reactogenicity event on days 1-8 after RZV dose 2 in the RZV and allV4 group vs. RZV and HD-IIV4 group.

The proportions of participants with at least one severe (Grade 3) solicited systemic reactogenicity event on days 1-8 after RZV dose 2 in the mITT Population will be compared between vaccine groups using the same statistical methodology as for Primary Objective 1. A one-sided site-stratified noninferiority test to determine if RZV dose 2 and allV4 is noninferior to RZV dose 2 and HD-IIV4 with the alpha level set at 0.025 and a 10% noninferiority margin.

This information will also be presented by age-group for the subset of subjects aged 65-69 versus those subjects aged 70 years or older. No formal statistical hypothesis testing (i.e., no p-values) will be performed, only the confidence boundary of the difference will be presented.

4. To compare the proportion of participants with at least one serious adverse event or adverse event of clinical interest after RZV dose 2 in the RZV and allV4 group vs. RZV dose 2 and HD-IIV4 group and describe these events through the entire study period.

The proportion and 95% exact binomial confidence interval in the ITT Population of serious adverse events and events of clinical interest through the entire study period will be presented by site, vaccine group, and relatedness. Listings of the serious adverse events will also be presented. Non-overlapping confidence boundaries will be an indication of a statistical difference between the vaccine groups.

5. To compare the proportion of participants with moderate-to-severe (Grade 2-3) solicited local or systemic reactogenicity event on days 1-8 after RZV dose 1 in the RZV and allV4 group vs. RZV dose 1 and HD-IIV4 group.

The proportions of participants with at least one moderate-to-severe (Grade 2-3) solicited local or systemic reactogenicity event on days 1-8 after RZV dose 1 in the mITT Population will be compared between vaccine groups using the same statistical methodology as for Primary Objective 1. A one-sided site-stratified noninferiority test to determine if RZV dose 1 and allV4 is noninferior to RZV dose 1 and HD-IIV4 with the alpha level set at 0.025 and a 10% noninferiority margin.

This information will also be presented by age-group for the subset of subjects aged 65-69 versus those subjects aged 70 years or older. No formal statistical hypothesis testing (i.e., no p-values) will be performed, only the confidence boundary of the difference will be presented.

6. To compare the proportion of participants with moderate-to-severe (Grade 2-3) solicited local or systemic reactogenicity event on days 1-8 after RZV dose 2 in the RZV and allV4 group vs. RZV dose 2 and HD-IIV4 group.

The proportions of participants with at least one moderate-to-severe (Grade 2-3) solicited local or systemic reactogenicity event on days 1-8 after RZV dose 2 in the mITT Population will be compared between vaccine groups using the same statistical methodology as for Primary Objective 1. A one-sided site-stratified noninferiority test to determine if RZV dose 2 and allIV4 is noninferior to RZV dose 2 and HD-IIV4 with the alpha level set at 0.025 and a 10% noninferiority margin.

This information will also be presented by age-group for the subset of subjects aged 65-69 versus those subjects aged 70 years or older. No formal statistical hypothesis testing (i.e., no p-values) will be performed, only the confidence boundary of the difference will be presented.

7. To compare serum hemagglutination inhibition (HAI) antibody titers after RZV dose 1 and HD-IIV4 with RZV dose 1 and allIV4 for each of the four influenza vaccine strains contained in the respective vaccine for that season in the full study population and by age.

The proportion of subjects achieving seroconversion at day 29 (an HAI titer > 1:40 at day 29 if the baseline titer is < 1:10 or a minimum four-fold rise in HAI titer if the baseline titer is > 1:10) for each influenza strain in the respective season's vaccine in each vaccine group will be presented along with the difference between vaccine groups and a 95% confidence interval of the difference in proportions.

The proportion of subjects with a seroprotective HAI titer ($\geq 1:40$) pre- and post-immunization at day 29 for each IIV antigen in the respective season's vaccine in each vaccine group will be presented along with a 95% confidence interval, as well as the difference between vaccine groups and a 95% confidence interval of the difference in proportions.

The geometric mean HAI titer (GMT) at Day 1 and Day 29 for each IIV antigen in the respective season's vaccine in each vaccine group will be presented along with a 95% confidence interval, as well as the difference between vaccine groups (on the log₁₀ scale) and a 95% confidence interval of the difference in GMTs for each vaccine group (on the log₁₀ scale).

The geometric mean fold rise (GMFR) in HAI titer at Day 29 for each IIV antigen in the respective season's vaccine in each vaccine group will be presented along with a 95% confidence interval.

This information will also be prepared by age-group (65-69 years and ≥ 70 years).

8. To describe and compare changes in health-related quality of life after RZV dose 1 and allIV4 with RZV dose 1 and HD-IIV4 in the full study population and by age-group (administered on study Day 60).

EQ-5D and EQ VAS Scale

The EQ-5D is a standardized, generic measure of health status that provides information on health-related quality of life and activities of daily living relevant to older adults: mobility, self-care, usual activities, pain/discomfort and anxiety/depression (<http://www.euroqol.org/>)

(23). In addition, the instrument contains the EQ Visual Analogue Scale (EQ-VAS) which measures the respondent's self-rated health.

The EQ-5D-5L is the new version of the EQ-5D that increases the levels of severity from three to five to significantly increase reliability and sensitivity while maintaining feasibility and reducing ceiling effects. The descriptive system comprises 5 dimensions of mobility, self-care, usual activities, pain/discomfort, anxiety/depression. For each of these dimensions, there are 5 response levels: no problems, slight problems, moderate problems, severe problems, and extreme problems. The respondent is asked to indicate his/her health state by ticking in the box against the most appropriate statement in each of the 5 dimensions. This decision results in a 1-digit number expressing the level selected for that dimension. The digits for 5 dimensions can be combined in a 5-digit number describing the respondent's health state from 11111 as best health and 55555 as worst health. These numbers are converted to a Utility Index that ranges from -0.109 (worst health) to 1.000 (best health) for US specific values. The minimum clinically important difference ranges from 0.05 to 0.1 depending on health conditions being studied. The EQ VAS records the respondent's self-rated health on a 20 cm vertical, visual analogue scale with endpoints labelled 'the best health you can imagine' (100) and 'the worst health you can imagine' (0). The respondent marks an 'X' on the scale number to indicate how their health is 'today.' The minimum clinically important difference on the VAS is 8.

The EQ VAS has a range of 0 (worst health) to 100 (best health).

Post-vaccination EQ-5D and EQ VAS index values will be calculated by the lowest/worst index value scores from baseline. The changes from baseline for the index values will be assessed within vaccine group using a linear regression model adjusting for site since these will follow a normal distribution. The VAS minimum clinically important difference is 8, so categorical comparisons (less than 8 points, within 8 points, greater than 8 points) will be made using a Mantel-Haenszel statistic in a stratified analysis by site. The Mann-Whitney U test (Wilcoxon rank-sum test) will be used to compare the difference scores from baseline between the two vaccine groups for the index values and VAS.

The statistical tests described above will also be performed by age-group (65-69 years and ≥ 70 years). This testing will be considered exploratory with an alpha level of 0.05 with no alpha adjustment.

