#### 7.1.4 Secondary and Exploratory Objectives

The statistical methodology described above for the Primary Objective will also be applied to all Secondary Objectives 1 and 2 and Exploratory Objectives 1, 2, 3, 5 and 6. For Secondary Objective 3 and Exploratory Objective 4, the proportion of participants with severe adverse events will be presented in a table along with exact 95% confidence intervals. The confidence intervals will be used to make comparisons and interpretations. For Exploratory Objective 7, seroconversion or seroprotection at day 29 will be compared using a Mantel-Haenszel statistic in a stratified analysis by site. HAI titer (GMTs) and the geometric mean fold rise (GMFR) in HAI titer will be compared using a regression model that will control for site or nonparametric testing if normality assumptions are not met.

For Exploratory Objective 8, the EQ-5D-5L responses are converted to a Utility Index that ranges from -0.109 (worst health) to 1.0 (best health) using the US specific value sets ([http://www.euroqol.org/fileadmin/user\\_upload/Documenten/Excel/Crosswalk\\_5L/EQ-5D-5L\\_Crosswalk\\_Value\\_Sets.xls](http://www.euroqol.org/fileadmin/user_upload/Documenten/Excel/Crosswalk_5L/EQ-5D-5L_Crosswalk_Value_Sets.xls)). The EQ VAS has a range of 0 (worst health) to 100 (best health). The changes from baseline will be assessed within vaccine group using a paired t-test for the index values and VAS. If normality assumptions are not met, the testing will be performed with a Wilcoxon signed-rank test. The Mann-Whitney U test (Wilcoxon rank-sum test) will be used to compare the difference scores from baseline between the two vaccine groups for the index values and VAS.

Proportions for all objectives will be presented in tables and the noninferiority comparisons will be presented in graphical displays as well. There will be no adjustment to the alpha level for these comparisons, with all noninferiority comparisons at the one-side alpha 0.025 level with a 10% noninferiority margin. The alpha level will be set at the two-side 0.05 level for Exploratory Objectives 7, 8, and 9.

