5.2 Analytic Issues

There are two sites participating in the study and analysis of the primary objective will be stratified by site (Duke University and Johns Hopkins University) to account for this unit of randomization. All objectives will be stratified by site when applicable. The alpha will be set at a one-sided 0.025 level for noninferiority testing and at the alpha 0.05 level otherwise. There will be no adjustments to the alpha level for multiple comparisons. Should an interim safety analysis be required, the alpha level will be adjusted to assure the overall type I error is maintained at the one-sided alpha 0.025 level for the primary outcome of non-inferiority.

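### Exploratory Objective 4 compares serious adverse events and events of clinical interest only by overlap of two 95% intervals, a rule with type I error below 0.5%, and omits the interval of the difference given for Secondary Objective 3

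*SAP*

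**What the plan says.** SAP 8.3, Exploratory Objective 4, sets out to compare the vaccine groups on the proportion with at least one "serious adverse event or adverse event of clinical interest after RZV dose 2". It reports a 95% exact binomial interval for each proportion in the ITT population; the results "through the entire study period will be presented by site, vaccine group, and relatedness". Serious adverse events are also listed. The only comparison rule is "Non-overlapping confidence boundaries will be an indication of a statistical difference between the vaccine groups". No difference between groups is reported, and no interval of a difference.

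SAP 8.2, Secondary Objective 3, covers the same event types through Day 43. It gives the same exact intervals "as well as the difference between vaccine groups and a 95% confidence interval of the difference in proportions". The method for that interval is not named.

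Protocol 7.1.4 treats the two objectives together: "For Secondary Objective 3 and Exploratory Objective 4, the proportion of participants with severe adverse events will be presented in a table", with exact 95% intervals. (It writes severe where the objectives write serious; I take the same events to be meant.) It adds: "The confidence intervals will be used to make comparisons and interpretations". It states no overlap rule.

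On error level, SAP 5.2 says "The alpha will be set at a one-sided 0.025 level for noninferiority testing and at the alpha 0.05 level otherwise", with no multiplicity adjustment. Protocol 7.1.4 names the two-sided 0.05 level only for Exploratory Objectives 7 to 9.

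**The concern.** Two 95% intervals can overlap while the 95% interval of the difference excludes zero. An overlap rule is therefore a much stricter test than the level on the intervals suggests. Nothing in either document indicates that a stricter level was wanted here, and the SAP gives no reason for handling the two objectives differently when the protocol gave them one method.

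This is the only planned between-group comparison of serious adverse events and new immune-mediated disease beyond Day 43, and the safety of combining two novel adjuvants is the reason for the trial. The rule errs towards silence: a real imbalance would often go unflagged, and readers may take overlap to mean no difference.

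A smaller point concerns the window. The objective concerns events after dose 2, but the analysis sentence gives only the end of the period. If counting starts at dose 2, events from Day 44 until dose 2 (Day 60, window 60 to 65) enter neither Secondary Objective 3 nor this objective. If it starts at Day 1, events through Day 43 enter both.

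**Working it through.** **Inputs.** The group sizes come from the sample size section (Protocol 7.1.1, SAP 4.3), and that calculation reproduces: n = (1.960 + 0.8416)² × 2 × 0.14 × 0.86 / 0.10² = 189.0, rounded up to 190 per group, 380 in total; 380 / 0.95 = 400, or 200 per group. The documents give no rate for serious adverse events or events of clinical interest, so every rate below is an assumption.

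**Large-sample size of the rule.** With equal groups and a common standard error SE, non-overlap needs a difference above 1.96 × 2 × SE. A 95% interval of the difference excludes zero above 1.96 × √2 × SE. The overlap rule therefore works at z = 1.96 × √2 = 2.772, and its two-sided type I error is 2 × (1 − Φ(2.772)) = 0.56%. Exact intervals are wider still, so the actual figure is lower.

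**Exact enumeration.** I took two independent binomials and summed the probability of every pair of counts that a rule flags. Because Secondary Objective 3 names no method, I set the overlap rule against two intervals of the difference (unstratified Newcombe, and Miettinen-Nurminen score) and one test (two-sided Fisher, p ≤ 0.05).

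Probability of flagging, 200 per group:

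| True rates | Overlap | Newcombe | Score | Fisher |
|---|---|---|---|---|
| 1% vs 1% (type I error) | 0.006% | 1.6% | 4.1% | 0.5% |
| 2% vs 2% (type I error) | 0.11% | 3.6% | 4.5% | 1.7% |
| 5% vs 5% (type I error) | 0.25% | 4.6% | 4.8% | 2.9% |
| 8% vs 2% | 42.0% | 81.1% | 81.7% | 75.1% |
| 5% vs 2% | 7.3% | 35.0% | 37.5% | 27.0% |
| 4% vs 2% | 2.6% | 18.9% | 21.0% | 13.1% |
| 2% vs 1% | 0.3% | 8.6% | 11.5% | 4.4% |

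At 190 per group, 8% vs 2% gives 38.5%, 78.8%, 79.8% and 72.2%. Searched over event rates, the largest type I error of the overlap rule is 0.43% at 200 per group and 0.47% at 190.

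**In counts, 200 per group.** Smallest number of affected participants in the other group that is flagged:

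| Affected in one group | Overlap | Newcombe | Score | Fisher |
|---|---|---|---|---|
| 0 | 9 | 5 | 4 | 6 |
| 2 | 14 | 9 | 9 | 10 |
| 4 | 18 | 12 | 12 | 13 |

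So 6 to 8 against 0, or 10 to 13 against 2, would be flagged by both intervals and by the Fisher test but not by overlap.

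**One case in full: 8 vs 0.** The exact interval for 0/200 has upper limit 1 − 0.025^(1/200) = 1.83%. The exact interval for 8/200 is 1.74% to 7.73%. Since 1.74% < 1.83%, they overlap and nothing is flagged. For Newcombe, the Wilson limits are 2.04% to 7.69% for 8/200 and 0 to 1.88% for 0/200, and the difference is 4.0 points:
- lower limit: 4.0 − √((4.0 − 2.04)² + 1.88²) = 1.3 points
- upper limit: 4.0 + (7.69 − 4.0) = 7.7 points

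The interval excludes zero, and the two-sided Fisher p is 0.007.

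**The case against.** The best defence is that little rides on this. The objective is exploratory. The SAP calls non-overlap only an indication and never says that overlap means no difference. The rule errs only towards caution. A reader with the counts can compute the interval of the difference. All of this stands, and it limits the weight of the point. It does not justify keeping a rule that performs much worse than the one used for Secondary Objective 3.

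The 0.05 benchmark can also be questioned: no test is specified for this objective, and the protocol's two-sided 0.05 does not name it. But the SAP's own general clause covers whatever is not noninferiority testing. Nor does the overlap sentence contradict the protocol, which only says that the intervals will be used for comparison. It is one way to do that, and a weak one.

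The striking gap needs a large difference. At 4% vs 2% the best alternative flags 21.0%, and at 2% vs 1% only 11.5%, so the change would not rescue small differences. At a 1% rate the Newcombe interval itself runs at 1.6%, so a true 5% is not what the overlap rule forgoes when events are rare.

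Two side points are weaker. Results are shown by site and relatedness as well as by group, and the sentence does not say which intervals are compared. However, it names the vaccine groups, so the overall comparison is the natural reading. (Read by site, with about 110 and 90 per group, 8% vs 2% would be flagged 15.5% and 8.7% of the time.) The counting window is largely settled by the endpoint wording in SAP 3.3, which refers to events after dose 2; the analysis sentence only needs to agree with it.

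**Conclusion.** The concern holds. The overlap rule has a two-sided type I error below 0.5% at every event rate and group size examined, against the SAP's 0.05, and the objective lacks the interval of the difference that its companion objective has. The bound does not depend on an assumed event rate. The power figures do: at 8% vs 2%, detection is about half of what an interval of the difference gives (42.0% against 81.1% for Newcombe), while small differences are mostly missed by any rule.

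The risk is a missed or understated safety signal after Day 43, not a false one. The primary conclusion is unaffected. The change should be made, but the trial does not depend on it.

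**What to change.** - Delete the overlap sentence from Exploratory Objective 4 and keep the exact interval per group that the protocol plans.
- Add the between-group difference with a 95% interval by one method fixed now and used whatever the counts turn out to be. The unstratified Newcombe interval with both sites combined is one choice, defined at any event count. Since SAP 5.2 says "All objectives will be stratified by site when applicable", state that this interval is not site-stratified. A site-stratified Newcombe interval, as in the primary analysis, would also serve; what matters is that one method is named.
- Name the same method for Secondary Objective 3.
- State in the analysis sentence whether events are counted from dose 2 or over the whole study. If events after dose 2 are also shown among those who received dose 2, label that display descriptive, because it conditions on something that happens after randomisation.

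The cost is SAP wording and one extra table column, with no new data and no protocol change.
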